**Table 14.3.2.14: Laboratory data over the whole study: Descriptive statistics of the actual values per time point**

**Table 14.3.2.15: Laboratory data over the whole study: Descriptive statistics of the changes from baseline per time point**

**Table 14.3.2.16: Laboratory data over the whole study: Descriptive statistics of the percent changes from baseline per time point**

**Table 14.3.2.17: Laboratory data over the whole study: Shift table of the lab abnormalities per time point**

**Table 14.3.2.18: Laboratory data over the whole study: Treatment-emergent lab abnormalities per time point**

**Table 14.3.2.19: Laboratory data over the whole study: Frequency table of the CTCAE toxicity grades per time point**

**Table 14.3.2.20: Laboratory data over the whole study: Shift table of the CTCAE toxicity grades per time point**

**Table 14.3.2.21: Laboratory data over the whole study: Treatment-emergent CTCAE toxicity grades per time point**

**Table 14.3.2.22: Laboratory data over the whole study: Frequency table of the ATP III classes per time point**

**Table 14.3.2.23: Laboratory data over the whole study: Shift table of the ATP III classes per time point**

**Table 14.3.2.24: Laboratory data over the whole study: Treatment-emergent ATP III classes per time point**

**Table 14.3.2.25: Laboratory data over the whole study: Frequency table of percent changes from baseline per time point in inhibin B and testosterone**

**Table 14.3.2.26: Laboratory data over the whole study: Shift table of the categorical lab data per time point**

### 12.2.12. Figures over the whole 24 weeks period

The follow-up visit will not be shown on the mean plots because it is expected that it will happen only for a limited number of subjects, as a large number will roll over into study 205 without a follow-up visit.

The same plots again, but with the 11 adapted treatment groups. Plots will show data from screening up to the end of the study.

**Figure 14.3.2.4: Laboratory data over the whole study: Subject profile plots over time – subjects with a treatment-emergent abnormality**

**Figure 14.3.2.5: Laboratory data over the whole study: Mean plots of the actual values over time**

**Figure 14.3.2.6: Laboratory data over the whole study: Mean plots of the changes from baseline over time**

**Figure 14.3.2.7: Laboratory data over the whole study: Mean plots of the percent changes from baseline over time**

### 12.2.13. Listings

All listings will contain next to the actual data (raw and changes) the following parameters:

- a fasted Y/N flag
- an abnormality L/H flag
- CTCAE toxicity grade, ATP III classification
- the test's normal range
- a clinical relevance flag

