#### **8.7.1.4.2 Clinical Laboratory Evaluation**

The hematology and clinical chemistry laboratory analyses will be performed at a central laboratory ([REDACTED]). Reference ranges will be supplied by the central laboratory and used by the investigator to assess the laboratory data for clinical significance and pathological changes.

The total amount of blood to be taken during the study will not exceed 600 mL.

The following laboratory safety tests will be performed at every visit:

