##### **Clinical Chemistry**

Creatinine, blood urea nitrogen (BUN), AST, ALT, gamma glutamyltransferase (GGT), alkaline phosphatase, total bilirubin, amylase, lipase, albumin, total protein, sodium, potassium, chloride, glucose, uric acid, total cholesterol, HDL and LDL, triglycerides, calcium, phosphorus, and CRP.

Serum pregnancy test for females of childbearing potential at Screening and Week 24 only/EDV only.

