### **8.8.1.8 Pharmacokinetic, Efficacy, Safety and Pharmacodynamic Correlations**

Exposure-efficacy response relationship between GLPG0634 and G254445 concentrations and selected efficacy endpoints such as CRP, and DAS28 will be explored. Correlation with safety parameters (i.e., neutrophils, LDL, or others) will be explored if altered by the treatments. More parameters may be used for the correlation if deemed necessary. [REDACTED]

The results of PK/PD, -efficacy, and –safety analyses will be reported separately.

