### 12.2.5.4. ATP III classifications

Lab test	Categories				
LDL (mg/dL)	< 100	[100,130[	[130,160[	[160,190[	≥ 190
HDL (mg/dL)	< 40	[40,60[	≥ 60		
Total cholesterol (mg/dL)	< 200	[200,240[	≥ 240		
Triglycerides (mg/dL)	< 150	[150,200[	[200,500[	≥ 500	

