**Table 14.3.2.9: Laboratory data up to Week 12: Frequency table of the ATP III classes per time point**

Frequency table (with cumulative percentages) per lab test category (hematology, biochemistry, endocrine, urinalysis), lab test, treatment group and time point.

Table for selected tests only.

Population: safety.

Table to be created for the Week 12 interim analysis as well.

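### Triglyceride and high-glucose classes ignore the fasting flag held with the lab data, which adds background noise to the shift tables in every arm

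*SAP*

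**What the plan says.** Protocol 8.7.1.4.2 introduces the laboratory panel with "The following laboratory safety tests will be performed at every visit". The chemistry list includes "glucose, uric acid, total cholesterol, HDL and LDL, triglycerides, calcium, phosphorus, and CRP". No fasting instruction appears there, in the visit procedures (8.6.1 to 8.6.3), in the dosing section (8.5.6) or in the flow chart (8.7.1.5).

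SAP 12.2.5.2 assigns CTCAE grades to triglycerides and to high glucose. SAP 12.2.5.4 assigns ATP III classes to triglycerides, with cut-offs at 150, 200 and 500 mg/dL. Neither separates fasted from fed samples.

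Fasting appears once in the two documents, in SAP 12.2.13, which opens with "All listings will contain next to the actual data (raw and changes) the following parameters" and then names "a fasted Y/N flag". The rules that build the tables do not use it:

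- Baseline is the last sample before first dose (12.2.4).
- When several visits fall in one window, the one nearest the target day is selected (3.4).
- A result is treatment-emergent if its CTCAE grade (Table 14.3.2.8) or ATP III class (Table 14.3.2.11) is higher than at baseline.
- The worst case is the highest post-baseline grade or triglyceride class, including unscheduled samples and those not selected for their window (12.2.8).

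**The concern.** Triglycerides and glucose can rise after a meal. If a subject is fasted at Baseline and fed at Week 4, the meal alone can move the result up a class, and the SAP will count that as treatment-emergent. In the opposite order, a real rise can be hidden. Over several visits, one fed sample is enough to set the subject's worst case.

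The stake is how readable the metabolic safety tables are. Four of the tables concerned are marked for the Week 12 interim: 14.3.2.6 and .8 (CTCAE), and 14.3.2.9 ("Frequency table of the ATP III classes per time point") and .11 (ATP III). SAP 6.2 says the interim supports preliminary dose selection for phase III. A higher background rate in every column makes a modest drug effect look smaller in relative terms.

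**Working it through.** The documents give no meal effect, fed-sample rate or triglyceride distribution, and state no figure to reproduce. The text check above is the finding. The arithmetic below only gives it scale.

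**Single-visit shift rate, triglycerides.** Inputs:

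- From SAP 12.2.5.4: cut-offs 150, 200 and 500 mg/dL.
- Assumed: median 120 mg/dL, between-subject log SD 0.45, within-subject CV 20%, no drug effect.
- Varied: meal effect *m*, and the share *f* of samples that are fed, the same at both visits and assigned independently.

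Model: ln TG = ln 120 + 0.45·Z(subject) + s·e(sample) + ln(1+m)·Fed, with s² = ln(1 + 0.20²). The quantity is P(post-baseline class > baseline class), by simulation.

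With all samples fasted the rate is 12.3%. At CV 15% to 25% it is 10% to 14%. With mixed sampling at CV 20%:

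| Meal effect | f = 10% | f = 20% | f = 50% |
|---|---|---|---|
| +20% | 13.0% | 13.6% | 14.8% |
| +30% | 13.4% | 14.5% | 16.3% |
| +40% | 14.0% | 15.4% | 18.0% |

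The increase over all-fasted runs from 13.0 − 12.3 = 0.7 to 18.0 − 12.3 = 5.7 points, so about 1 to 6 points per visit.

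**Why the increase is not larger.** Among pairs that go from fasted to fed, the shift rate is 19%, 26%, 34% and 41% for meal effects of +10%, +20%, +30% and +40%. Such pairs are only f(1−f) of all pairs: 9%, 16% and 25% at f = 10%, 20% and 50%. At f = 20% and +30% they add about 0.16 × (34 − 12) = 3.5 points. The equally frequent fed-to-fasted pairs shift up less often and give part of that back. The net is 14.5 − 12.3 = 2.2 points.

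**Effect on the comparison at one visit.** With an assumed 15% drug-induced rise, 20-50% of samples fed and a +20% to +30% meal effect, the drug-minus-placebo difference stays near 10 points. The ratio falls from about 1.8 to 1.6-1.7.

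**Accumulation in the worst case.** Let *q* be the assumed chance that a meal alone raises the class at a visit. Treating visits as independent, the rate over *k* visits is 1 − (1−q)^k. There are 5 scheduled post-baseline visits to Week 12 and 8 to Week 24.

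| q | k = 5 | k = 8 |
|---|---|---|
| 1% | 4.9% | 7.7% |
| 2% | 9.6% | 14.9% |
| 5% | 22.6% | 33.7% |

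In an arm of 85, the k = 5 column is about 4, 8 and 19 subjects. All visits share one baseline sample, so independence probably overstates the accumulation.

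To show the dilution, assume true drug-related rates of 5% and 15% and the 22.6% background. They become 1 − 0.95 × 0.774 = 26.5% and 1 − 0.85 × 0.774 = 34.2%. The difference falls from 10 to 7.7 points and the ratio from 3.0 to 1.3.

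Nothing was calculated for glucose. It is included because its grades are built by the same rules.

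**The case against.** The strongest reply is that this does not distort the comparison. The trial is randomised and double-blind, so fed sampling should be similar across arms. The placebo column shows the background, the lab tables carry no p-values, and the listings let a reader check individual shifts. All of that stands, and it is why the point is minor.

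Several stronger readings are tempting, and the documents do not support them:

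- *A reader might take 19-41% as the shift rate.* That needs every baseline sample fasted and every later one fed. The protocol words chemistry sampling alike at Baseline and later visits, so nothing suggests such a one-way pattern.
- *A reader might extend the point to LDL.* Protocol 6.1 names LDL and HDL rises with another JAK inhibitor. But the effect of a meal on reported LDL depends on whether it is calculated from triglycerides or measured directly, which is not stated.
- *A reader might link it to the exposure analyses.* Protocol 8.8.1.8 says "Correlation with safety parameters (i.e., neutrophils, LDL, or others) will be explored if altered by the treatments". That is conditional, the analyses belong to a separate SAP (6.1.6), and SAP 6.3.2 removed the plots of plasma level against lab safety. Nothing indicates they would use these classes.
- *A reader might suppose that all these tables feed the interim.* Of those at issue, only 14.3.2.6, .8, .9 and .11 are marked. Shift tables 14.3.2.7 and .10 and the 24-week tables are not.
- *A reader might want fasted pairs to replace the main analysis.* That conflicts with SAP 4.6, which keeps all measured values, and with the inclusive worst-case rule in 12.2.8. It could also hide genuine elevations.

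Finally, the absence of a fasting rule is inferred from silence. A laboratory manual or the mock tables, neither supplied, may contain one. The flag shows that status is recorded, not how much it varies.

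**Conclusion.** The point holds as a minor, inexpensive improvement. As written, the SAP can count a fasted-to-fed change as a treatment-emergent triglyceride or high-glucose shift, and a single fed sample can set the worst case.

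For triglycerides the inflation is about 1 to 6 points per visit in every arm. That rests on the assumed distribution, 10-50% of samples fed at both visits and a +20% to +40% meal effect. It is larger in the worst-case columns, by an amount that depends on an assumed per-visit rate and on independence between visits. The between-arm ratio weakens, while the single-visit difference is largely preserved. There is no directional bias between arms, and no effect on the primary endpoint.

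**What to change.** Keep the all-samples tables, including worst case, exactly as planned. In SAP 12.2.9 and 12.2.11:

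1. Add a supportive version of the triglyceride rows (ATP III and CTCAE) and the glucose-high rows (CTCAE) in the frequency, shift and treatment-emergent tables. Restrict it to pairs in which both the baseline and the post-baseline sample are flagged fasted.
2. Report the number of fasted samples per arm and visit, so that a reader can judge how far mixing matters.
3. For the Week 12 interim, add the supportive rows to Tables 14.3.2.6, .8, .9 and .11.
4. Include LDL only if it is calculated from triglycerides, and state the method.

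If a laboratory manual already sets a fasting rule, cite it in the SAP.

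The cost is a filter on a flag already in the data, a paragraph of SAP text, and a few extra rows with smaller denominators. Nothing new is collected and trial conduct does not change.

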#### **Listing 16.2.11.1: Laboratory data: Full listing**

Listing per treatment group, per subject and per time point of all recorded data.

Population: safety.

#### **Listing 16.2.11.2: Laboratory data: Abnormalities listing**

Listing per treatment group, per subject and per time point of all post-baseline data scored as out-of-normal-range, plus also the baseline reference time point.

Population: safety.

#### **Listing 16.2.11.3: Laboratory data: Clinically significant abnormalities**

Listing per treatment group, per subject and per time point of the eCRF's verbatim text field on clinically significant abnormalities.

Population: safety.

#### **Listing 16.2.11.4: Laboratory data: Urinalysis results**

Listing per treatment group, per subject and per time point of the abnormal urinalysis results only (including the baseline result as reference).

Population: safety.

#### **Listing 16.2.11.5: Laboratory data: Positive pregnancy tests**

Listing per treatment group, per subject and per time point of all pregnancy test results (urine and serum) for female subjects who had a positive test at some point.

Population: safety.

### **12.3. ECG**

#### **12.3.1. Available Data**

Available parameters: HR, QRS, QT, and an interpretation. The RR interval, when available, will only be listed.

#### **12.3.2. Calculated Parameters**

The QTc will always be derived during the statistical analysis, even when already available in the database. The value in the database will not be used in the analysis.

The QTc will be calculated using the following formula: Fridericia's cube-root corrected QT (Fridericia, 1920):

$$QTcF \text{ (ms)} = QT \text{ (ms)} \times \sqrt[3]{\frac{HR(bpm)}{60}}$$

The QTcF will be rounded up to the nearest integer prior to the derivation of changes and categorizations.

#### **12.3.3. Baseline and Change from Baseline**

The baseline is defined as the last nonmissing value prior to dosing. Baseline will be determined per ECG parameter individually. It is recognized that baseline parameters may thus come from more than one ECG reading and not just from the "baseline visit" reading.

The change from baseline will be calculated for all post-baseline time points as:

Change from baseline at time point t = value at time point t – baseline value.

#### **12.3.4. Visits for analysis**

An ECG is only taken at Screening (baseline), Week 12, Week 24/EDV and Follow-up. Therefore the analysis will not use any time windowing, but will just present the visits as they are: Baseline, Week 12 and Week 24, and Follow-up. See also mocks.

In case the subject prematurely discontinues the study during the first period of the study, the EDV ECG will be used as “Week 12”. In case the subject prematurely discontinues the study during the second period of the study, the EDV ECG will be used as “Week 24”.

Because of this, there will not be a “last on-treatment” nor a “worst-case”.

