#### **4.6. HANDLING OF OUTLIERS**

All measured values will be included in the analyses.

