### **12.2.8. Worst-Case Abnormality**

Derived per parameter separately, for abnormalities only.

Three worst-case determinations will be done, depending on the chapter of analysis:

1. Including all nonmissing post-baseline values, including “use=No” and unscheduled measurements, up to and including the Week 12 value. Also including the follow-up value in case the subject did not participate in the second period of the study. If the subject participated in the second period of the study, then the follow-up value will be included in the worst-case of the second period of the study, not of the first period.
2. Including all nonmissing post-Week 12 values, including “use=No” and unscheduled measurements, up to and including the follow-up value.
3. Including all nonmissing post-baseline values, including “use=No” and unscheduled measurements, up to and including the follow-up value.

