#### **Table 14.3.3.3: ECG at Week 12: Shift table of the QT abnormalities**

Shift table per test, treatment group and time point. The table will present the shift in abnormality at each post-baseline time point (including the worst-case) versus the baseline abnormality. Parameters: QT and QTcF.

Population: safety.

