**Table 14.3.3.4: ECG at Week 12: Treatment-emergent QT abnormalities**

Frequency table of the treatment-emergent abnormalities per parameter and treatment group. A post-baseline abnormality is considered treatment-emergent if it is higher than the baseline result. Parameters: QT and QTcF.

Population: safety.

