**12.3.7. Analysis tables for the whole 24 weeks period**

Repeat tables, population=safety, with the adapted treatment groups focusing on subjects who used GLPG0634 during both study periods:

**Table 14.3.3.7: ECG over the whole study: Descriptive statistics of the actual values per time point****Table 14.3.3.8: ECG over the whole study: Descriptive statistics of the changes from baseline****Table 14.3.3.9: ECG over the whole study: Shift table of the QT abnormalities****Table 14.3.3.10: ECG over the whole study: Treatment-emergent QT abnormalities****Table 14.3.3.11: ECG over the whole study: Treatment-emergent abnormal change in QT****Table 14.3.3.12: ECG over the whole study: Frequency table of the eCRF ECG interpretation per time point**

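### The ECG section of the SAP both rules out and requires a QT worst case, so an unscheduled on-treatment ECG may not reach the QT tables

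*SAP*

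**What the plan says.** SAP 12.3.4 starts from a premise about when ECGs exist: "An ECG is only taken at Screening (baseline), Week 12, Week 24/EDV and Follow-up". From this it draws the display rule: "Therefore the analysis will not use any time windowing, but will just present the visits as they are: Baseline, Week 12 and Week 24, and" (the last visit in that list is the Follow-up). An early discontinuation ECG is relabelled Week 12 or Week 24 according to the period in which the subject stopped. The section closes with "Because of this, there will not be a “last on-treatment” nor a “worst-case". SAP 3.3, whose windows would otherwise catch unscheduled visits, sends ECGs to section 12.3 instead.

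Two pages on, the specification of Table 14.3.3.3 reads: "The table will present the shift in abnormality at each post-baseline time point (including the worst-case) versus the baseline abnormality". SAP 12.3.7 then says "Repeat tables, population=safety, with the adapted treatment groups", so Table 14.3.3.9 takes over the same specification for 24 weeks.

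The tables that count new QT findings are specified differently. Table 14.3.3.4 is a "Frequency table of the treatment-emergent abnormalities per parameter and treatment group", and neither it nor Table 14.3.3.5 (categories of change) mentions a worst case. Tables 14.3.3.10 and 14.3.3.11 repeat them over 24 weeks.

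For laboratory data, SAP 12.2.8 defines three worst cases (period 1, period 2, whole study), the last being: "Including all nonmissing post-baseline values, including “use=No” and unscheduled measurements, up to and including the follow-up value". SAP 12.4.5 uses the same rules for vital signs.

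**The concern.** A programmer given 12.3.4 and the specification of Table 14.3.3.3 has to break one of them, and has no definition of an ECG worst case to fall back on. The choice decides whether an ECG recorded on drug outside the scheduled visits is summarised anywhere.

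QT is thinly sampled here: at most two scheduled on-treatment ECGs in 24 weeks. The categories that matter most (above 500 ms, or a rise above 60 ms) are read as counts of subjects, where one subject more or less is visible. If the only long QTcF in an arm was recorded at an unscheduled ECG, the categorical tables could show zero for that arm. The off-drug Follow-up ECG, taken 7 to 10 days after Week 24 or the early discontinuation visit (Protocol 8.6.3), would still have its own time point.

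**Working it through.** The plan states no figure on this point, so there is none to reproduce. The check sets the texts side by side and then follows one constructed subject through each reading.

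**Step 1: where an unscheduled on-treatment ECG would appear.**

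| Reading | Shift tables 14.3.3.3, 14.3.3.9 | Treatment-emergent and change tables 14.3.3.4, 14.3.3.5, 14.3.3.10, 14.3.3.11 | Listings 16.2.12.1, 16.2.12.2 |
|---|---|---|---|
| 12.3.4 governs | no | no | yes (in 16.2.12.2 if abnormal or clinically significant) |
| Worst case in the shift table, taken from displayed visits only | no | no | yes |
| Worst case in the shift table, defined as in 12.2.8 | yes | no | yes |

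Under all three readings the treatment-emergent and change tables leave it out.

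**Step 2: is the premise of 12.3.4 secure?** The protocol schedules ECGs only at the visits that 12.3.4 names. But SAP 12.3.3 accepts that baseline parameters may come from more than one ECG reading, so the SAP itself allows for extra ECGs before dosing. Protocol 8.3.4 lists clinically significant ECG results among the events that may end participation. An ECG between scheduled visits is therefore foreseeable, though none is planned.

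**Step 3: illustration with assumed values.** The SAP 12.3.2 formula is QTcF = QT × (HR/60)^(1/3), rounded up.

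| ECG | QT (ms) | HR (bpm) | QTcF (ms) | Category (ms) |
|---|---|---|---|---|
| Baseline | 400 | 65 | 411 | ≤450 |
| Unscheduled, Day 40, on drug | 485 | 70 | 511 | >500 |
| Week 12 | 410 | 66 | 424 | ≤450 |
| Week 24 | 412 | 66 | 426 | ≤450 |
| Follow-up | 405 | 65 | 416 | ≤450 |

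- Under 12.3.4 the highest tabulated post-baseline value is 426 ms and the largest rise is 426 − 411 = 15 ms. The subject counts as 0 above 500 ms and 0 above a 60 ms rise.
- A worst case drawn from the displayed visits only gives the same result.
- A worst case that includes unscheduled readings gives 511 ms and a rise of 511 − 411 = 100 ms. The subject counts in both top categories.

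**Step 4: size.** With 85 subjects per arm (Protocol 8.5.4 and 8.8.2), one subject is 1/85 = 1.2%, against 0%. This takes all 85 as treated with ECG data. In the 24-week tables some arms are split by the Week 12 switch, so the denominators there are smaller.

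**The case against.** The strongest reply is that 12.3.4 is coherent on its own terms. Laboratory tests and vital signs are taken at every visit, so a worst case condenses many values. Each period has one planned on-treatment ECG, so a period-level worst case over planned ECGs is that same ECG. On this view the words in Table 14.3.3.3 are left over from another section, and deleting them settles the matter. An abnormal ECG would in any case be listed and could be reported as an adverse event. A subject who discontinued would have the early discontinuation ECG tabulated as Week 12 or Week 24. The mock tables, a separate document not available here, may also settle the display.

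Most of this stands as a limit on the point. It does not remove the contradiction, and it does not say where an unscheduled ECG goes if one is recorded. Over the whole study there can be two planned on-treatment ECGs, so even then a worst case is not redundant.

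Three stronger readings are tempting and are not supported:

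- A reader might infer that an unscheduled ECG is missing from every QT table. That holds only if 12.3.4 governs, or if the worst case is confined to displayed visits. Under the laboratory definition it would appear in Tables 14.3.3.3 and 14.3.3.9. The exclusion is also implied by a closed list of visits; no sentence states it.
- A reader might infer a breach of SAP 4.6, "All measured values will be included in the analyses". That section concerns outliers. It stops extreme values from being deleted and gives no reading a place in a table.
- A reader might infer that the QT conclusion by dose will be wrong. The documents give no number of unscheduled ECGs and no QT results, and the ECG analysis is descriptive with no p-values.

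**Conclusion.** The contradiction between 12.3.4 and Table 14.3.3.3 (with its repeat, 14.3.3.9) is plain from the text. The treatment-emergent and change tables have a gap under any of the readings, and in this the ECG section departs from the rule that the SAP applies to laboratory data and vital signs.

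The consequence is conditional. It needs an unscheduled on-treatment ECG to be recorded, with a category worse than at the displayed visits. Where that happens to one subject in an arm of 85, the count above 500 ms reads 0% instead of 1.2%. How often it would happen cannot be estimated from the documents.

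The point does not touch the primary efficacy analysis. It is more than a clerical slip, because it decides whether the categorical QT tables can show zero when a long QTcF was recorded on drug. The SAP should be changed.

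**What to change.** Replace the last sentence of SAP 12.3.4 with a definition along these lines: for QT and QTcF, the on-treatment worst case is the highest value, and separately the largest increase from baseline, over all on-treatment post-baseline ECGs, including unscheduled and early discontinuation readings. Derive it for period 1, period 2 and the whole study, assigning each ECG by its date relative to the Week 12 visit.

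Keep Follow-up as its own time point, outside the worst case. The wording of 12.2.8 should not be copied unchanged, because it includes the Follow-up value and would mix off-drug readings into an on-treatment summary.

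Show the worst case in Tables 14.3.3.3 to 14.3.3.5 and 14.3.3.9 to 14.3.3.11, and align the mock tables.

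The lesser alternative is to delete the worst-case wording from Table 14.3.3.3 and state that unscheduled ECGs are only listed. That removes the contradiction but leaves the gap in the QT category tables.

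The cost is SAP wording and minor programming (one derived record per parameter, subject and period), with no new data. The downside is slightly higher QT abnormality counts.
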